#### 4.2 VGT-309 Proposed Dose

The dose for this study is 0.32mg/kg of VGT-309.

#### 4.3 VGT-309 Preparation

VGT-309 is stored frozen and must be thawed at room temperature for at least 30 minutes but not more than 2 hours before it is prepared for dosing.

#### 4.4 VGT-309 Dose Administration

VGT-309 will be given as an IV infusion, utilizing a syringe pump, over 15 to 20 minutes between 12-36 hours prior to start of the planned surgery.

#### 4.5 VGT-309 Storage and Accountability

VGT-309 will be stored frozen (-25 to -15°C) in a secure, locked area under the responsibility of the clinical research unit pharmacy or its designee.

The Investigator or Investigational Pharmacy must maintain accurate records of the receipt of all study drug, including date received, lot number, amount received, condition of the package and the disposition. Dispensing records will be maintained including the date and amount of study drug dispensed and the identity of the subject receiving the study drug.

Following dosing, all empty vials will be retained until reconciliation with the dispensing and shipping records is complete. Empty vials may then be destroyed using investigative pharmacy policy.

Following final reconciliation, unused study drug may either be destroyed according to site guidelines or returned to Vergent Bioscience, Inc., or designee.

#### 4.6 VGT-309 Packaging and Labeling

Labels will be in compliance with all applicable regulatory requirements for the labeling of active pharmaceutical ingredients according to Annex 13 of GMP. Specifically, labels will contain:

- “Limited by Federal Law to Investigational Use” statement.
- Study Drug name, route of administration and amount of VGT-309 in the vial.
- Lot number.

- Storage conditions.
- Sponsor name (Vergent Bioscience, Inc).
- Manufacturer.

## 5. SUBJECT POPULATION

### 5.1 Enrollment

This study plans to enroll a total of 40 subjects scheduled to undergo standard of care surgical resection for a lung nodule that is suspected or proven to be of concern to ensure at least 38 evaluable subjects.

[REDACTED]

### 5.2 Inclusion Criteria

In order to be enrolled in the study, the subject must:

1. Be willing and able to sign the informed consent and comply with study procedures.
2. Be at least 18 years of age.
3. Be male or female and meet the following conditions:
  - a. Female participants must be of non-childbearing potential, or,
  - b. If of childbearing potential be non-pregnant or lactating and agree to use highly effective contraception from screening through Day 30.
  - c. Male participants, if not surgically sterilized, and if engaging in sexual intercourse with a female partner of childbearing potential, must be willing to use highly effective contraception from screening through 30 days post-dose and agree not to donate semen during this waiting period.
  - d. Highly effective contraception involves the use of a condom for the male, plus one of the following for the female:
    - Oral, injectable, implantable, intravaginal, or transdermal hormonal contraceptives, or
    - Intrauterine device or intrauterine hormone-releasing system.

NOTE: Participants who abstain from heterosexual intercourse as their usual and preferred lifestyle, will not be required to use contraception as described above. They are required to maintain abstinence from screening through Day 30, AND

Participants in a same sex relationship, must use a barrier form of contraception (e.g., condom, diaphragm) to protect against the transfer of the study drug in any bodily fluids.

4. Have a lung nodule or mass that might be considered primary lung cancer or lung metastases, whether or not it is biopsy-proven.
5. Be scheduled to undergo standard of care surgical resection for a lung nodule or mass with diagnostic and/or curative intent for lung cancer and meet all pre-operative surgical and anesthesia acceptance criteria.
6. [REDACTED]
7. Have an ECOG score of 0-2.
8. Meet all standard surgical and general anesthesia requirements.
9. Have not participated in a clinical trial within the last 30 days.

### 5.3 Exclusion Criteria

Subjects may not be enrolled in the study if they:

1. They are not a candidate for standard of care surgery based on opinion of the surgeon, anesthesiologist, or other consulting physician.
2. They have a known allergy or reaction to ICG, other radiographic contrast agent, or any component of VGT-309.
3. [REDACTED]
4. They are prisoners, institutionalized individuals, or are unable to consent for themselves.
5. Have any other co-morbidity or habit that the Investigator believes will interfere with their ability to comply with and complete the study.

### 5.4 Replacement of Subjects

Subjects who withdraw consent prior to receiving VGT-309 will be replaced. Subjects not meeting the evaluable criteria (having received VGT-309 and NIR imaging) *may* be replaced. Additional subjects may be added if determined necessary to adequately evaluate safety.

## 6. STUDY PROCEDURES

Refer to Attachment A: Schedule of Assessments

### 6.1 Study Visits

Up to 3 in-clinic/hospital visits and 1 follow up phone call are planned for this study. Additional visits may be added if follow up for an adverse event is needed or if screening cannot take place in a single visit. Investigators should schedule visits within the protocol-specified timelines unless they receive permission from Vergent, or unforeseeable events prevent the subject from complying.

For a complete schedule of study procedures, refer to the Schedule of Assessments presented in Attachment A. All study procedures must be recorded in source documentation (primary occurrence of a record) maintained by the clinical site.

#### 6.1.1 Informed Consent

Prior to performing any study-related activities under this protocol, including screening tests and assessments, written informed consent with the IRB-approved ICF must be obtained from the subject in accordance with local practice and regulations.

All subjects must be provided a written Informed Consent Form (ICF) describing the study with sufficient information for them to make an informed decision regarding their participation. Subjects will be given the opportunity to ask questions about the study prior to participation.

A copy of the ICF, signed and dated by the subject, must be given to the subject and documented in the subject's source documentation. The original signed consent form will be retained with the study records.

#### 6.1.2 Screening (Days -60 to -1)

Once informed consent is obtained the following assessments will be done to establish a subject's eligibility for the study. Note: in cases where subjects have given consent for general pre-screening at the site, some of these assessments may be done by chart review.

When possible, the assessments should be done in the order listed here to avoid the demands of sample collection and ECG prior to the subject passing basic entry criteria requirements.

1. Review of eligibility requirements – inclusion and exclusion criteria.
2. Collection of demographic information and medical and surgical history, including review of prior and ongoing medications (taken in previous 30 days).
3. Physical Exam.
4. Height and weight measurements.
5. Vital signs measurement (blood pressure, pulse rate, respiratory rate and oral/tympanic temperature).
6. Standard 12-lead ECG (subject should be resting in a supine position for at least 5 minutes prior).
7. Blood sample collection for clinical chemistry, hematology and coagulation.
8. Urine sample collection for urinalysis.
9. In women of child-bearing potential, blood sample for serum pregnancy test.

Upon establishment of eligibility, subjects will be assigned to a dose and scheduled for admission to the hospital.

#### **6.1.3 Day 1: VGT-309 Dosing**

Subjects will check in to the hospital or infusion center as scheduled. After confirming their eligibility by reviewing their medical history and concomitant medications for any changes since screening, those subjects still considered eligible will undergo the following:

1. Targeted Physical Exam (Focus on heart, lungs and any area of change since screening).
2. Measurement of weight (ONLY if not done within 7 days prior to dosing).
3. Review of concomitant medications.
4. Vital signs measurement (blood pressure, pulse rate, respiratory rate and oral/tympanic temperature).
5. Standard 12-lead ECG (subject should be resting in a supine position for at least 5 minutes prior) (ONLY if not done within 4 weeks prior to dosing).
6. In women of child-bearing potential, blood sample for pregnancy test.
7. Blood sample for chemistry, hematology, coagulation. (ONLY if not done within 4 weeks prior to dosing).
8. Urine sample collection for urinalysis (ONLY if not done within 4 weeks prior to admission).
9. VGT-309 dosing to take place at 12-36 hours prior to induction of general anesthesia. (Refer to Section 4: Study Drug – VGT-309, for instruction on dose preparation and dosing procedures).
10. Upon dosing, VGT-309 subjects:
  - Will be observed and queried for possible adverse events.
  - Will have ECGs taken immediately after and 30 minutes after infusion ends.
  - Will have vital signs taken at 30 minutes and 2 hours after infusion ends.

#### **6.1.4 Day 1 or 2: Surgery and Pathology**

Following dosing with VGT-309, subjects will undergo planned standard of care surgical resection for their lung nodule or mass followed by pathological assessment of the resected tumor(s) and/or nodule(s) (Refer to Section 8: Efficacy Evaluations, for details).

### **6.1.5 Day 3: In-hospital follow up**

The day after surgery (between 24 to 48 hours after surgery), subjects will undergo the following:

1. Targeted Physical Exam (Focus on heart, lungs and any area of change since screening).
2. Review of concomitant medications.
3. Vital signs measurement (blood pressure, pulse rate, respiratory rate and oral/tympanic temperature).
4. Blood sample for chemistry, hematology, coagulation.
5. Urine sample collection for urinalysis.
6. Observation for and solicitation of adverse events.

### **6.1.6 Day 14 +/- 2 days: Telephone follow up**

Each subject will be contacted by telephone by a designated member of the study team, to inquire as to their general well-being, query for possible adverse events and any changes in their use of concomitant medications. If deemed necessary, a subject may be asked to return to the clinic for treatment or assessment of a possible adverse event.

### **6.1.7 Days 19 - 39: End of Study Follow up -OR- Early withdrawal**

This visit may be conducted in clinic or by telehealth visit. During this visit or if the subject withdraws from the study early, the following assessments will be done:

1. Review of concomitant medications for changes since last visit.
2. Observation for and solicitation of adverse events.

Following completion of these assessments, subjects will be released from the study. Additional follow-up may be necessary if an SAE is reported and has not yet resolved (See Section 10.2.2 for details).

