### 3. STUDY DESIGN

This is a Phase 2, open-label study to evaluate the safety and efficacy of VGT-309, a tumor-targeted, activatable fluorescent imaging agent, to identify cancer in subjects undergoing lung cancer surgery. [REDACTED]

Following agreement with and signing of the informed consent, subjects will undergo screening and baseline measurements for the study. Assessments include the following unless they have been done within 4 weeks prior to the anticipated dosing:

1. Medical, surgical and medication history.
2. Complete physical exam, including vital signs, height and weight.
3. Standard pre-operative chemistry, hematology, coagulation and urinalysis clinical laboratory studies.
4. 12-lead ECGs.
5. Serum pregnancy test for females of child-bearing potential.

Following clearance of all enrollment criteria, each subject will receive an IV administration of [REDACTED] VGT-309 at 12-36 hours prior to surgery (See Section 4 – Study Drug – VGT-309). Upon dosing, subjects will be observed for up to 2 hours and asked about possible treatment emergent adverse events.

Subjects will undergo surgical resection as planned and within the time specified following VGT-309 dosing. Measurements of efficacy will be taken during surgery and during the pathological examination of all surgical specimens.

Following surgery, subjects will be monitored for safety during their hospital stay. After discharge from the hospital, and approximately 14 days post-surgery, the subjects will be contacted by telephone to assess their well-being. Between 19 to 39 days post-surgery, subjects will either return to the clinic or participate in a telehealth visit for final safety assessments. If there are no adverse events requiring further follow up, subjects will be released from the study.

If a subject chooses to withdraw from the study prior to the final visit, they will be asked to undergo a final safety assessment before their departure.

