**NOTE: The study may also be stopped or delayed by the DSC as outlined in Section 9.1.2.**

### **7.1 Individual Subject Withdrawal**

The participation of an individual subject in the study may be terminated in the following circumstances:

1. Withdrawal of informed consent by the subject.
2. Any occurrence that, in the Investigator's opinion, makes continued participation contrary to the subject's best interests.

If an Investigator removes a subject from the study, or if a subject declines further study participation, an Early Withdrawal Visit, consisting of the assessments required at the Day 30 visit, will be completed as soon as possible. It will be the responsibility of the Investigator to ensure that all withdrawn subjects receive appropriate follow-up and medical care if needed.

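### The end-of-study contact has three inconsistent windows, each of which permits the last planned adverse event query 9 to 12 days before the 30-day SAE reporting period ends (minor, cheap to fix)

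*Protocol*

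**What the plan says.** The final contact is timed differently in different places:

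- Protocol 6.1.7 is headed "Days 19 - 39: End of Study Follow up -OR- Early withdrawal", in study days.
- Protocol Section 3 counts from the operation: "Between 19 to 39 days post-surgery, subjects will either return to the clinic or participate in a telehealth visit". The synopsis and SAP 3 use the same post-surgery range.
- Protocol 9.2.1 and 9.2.1.2 place the end-of-study visit on Days 22-36 and make it the end of adverse event documentation.
- Protocol 7.1 describes the early-withdrawal visit as "consisting of the assessments required at the Day 30 visit", although no visit is scheduled under that name in the readable text.

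Protocol 6.1.3 makes Day 1 the dosing day, and Section 4.4 has the infusion given "between 12-36 hours prior to start of the planned surgery". Section 9.2.2 requires SAEs up to 30 days post-dose to be reported once the site becomes aware of them.

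The contacts are limited: "Up to 3 in-clinic/hospital visits and 1 follow up phone call are planned for this study". The call is at Day 14 plus or minus 2 days (6.1.6). After the final contact, 6.1.7 states: "Following completion of these assessments, subjects will be released from the study". Section 3 makes release conditional: "If there are no adverse events requiring further follow up, subjects will be released from the study". SAP 9.1 defines a TEAE by its start relative to dosing, with no end day.

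**The concern.** There are two linked problems. First, sites have no single window to work to. A visit on Days 19-21 or 37-39 satisfies 6.1.7 but lies outside the window in 9.2.1. A visit 39 days after surgery satisfies Section 3 but falls after Day 39, the limit in 6.1.7. SAP 7.2 summarizes deviations as major or minor, so the same visit may or may not count as one, depending on the section consulted.

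Second, the protocol sets a 30-day post-dose period for SAEs but allows the last planned query before that period closes. No later contact appears in the readable text. A new SAE that starts after an early final visit depends on the site hearing of it by chance.

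Safety and tolerability are a stated objective, reported as percentages of subjects with events. Those percentages would pool subjects actively questioned for anything from about 18 to about 40 days after dosing.

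**Working it through.** The plan states no figure for this point, so the check is day counting followed by a sizing on assumed rates.

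**Inputs from the documents.** Dosing is Day 1 and screening ends at Day -1, so Day n is n - 1 days post-dose, and 30 days post-dose is Day 31. Surgery follows dosing by 12-36 hours, so days post-surgery convert to days post-dose by adding 0.5 to 1.5.

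**Gap = 30 - days post-dose at the last contact (zero if negative).**

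| Window | Days post-dose | Gap at earliest day | Gap at mid-window | Visit days before day 30 |
|---|---|---|---|---|
| Days 19-39 | 18 to 38 | 12 | 2 | 12 of 21 |
| 19-39 days post-surgery | 19.5-20.5 to 39.5-40.5 | 9.5-10.5 | 0-0.5 | 10-11 of 21 |
| Days 22-36 | 21 to 35 | 9 | 2 | 9 of 15 |

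Both study-day windows are centred on Day 29, which is 28 days post-dose. If Day n is read loosely as n days post-dose, the earliest-day gaps for the two study-day windows become 11 and 8.

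**Average gap if visits are spread evenly over the window (assumed).**

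- Days 19-39: (12 + 11 + ... + 1)/21 = 78/21 = 3.71 days.
- Post-surgery, surgery at 12 hours: (10.5 + ... + 0.5)/21 = 60.5/21 = 2.88 days.
- Post-surgery, surgery at 36 hours: (9.5 + ... + 0.5)/21 = 50/21 = 2.38 days.
- Days 22-36: (9 + ... + 1)/15 = 45/15 = 3.0 days.

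**Expected subjects affected.** The assumptions, none of them from the documents, are:

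- 80-95% of 30-day events start by day 14, and the remaining 5-20% are spread evenly over the 16 days from 14 to 30.
- The event risk is 10% in 40 subjects, so 4 subjects have an event.

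Share of events after the last contact = (0.05 to 0.20) x gap/16. Subjects = share x 4.

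- Evenly spread visits: 0.05 x 2.38/16 = 0.74% to 0.20 x 3.71/16 = 4.64%, or 0.03 to 0.19 subjects.
- All seen mid-window: 0 to 0.20 x 2/16 = 2.5%, or 0 to 0.10 subjects.
- All seen on the earliest day: 0.05 x 9/16 = 2.8% to 0.20 x 12/16 = 15%, or 0.11 to 0.60 subjects.
- Constant risk over 30 days, evenly spread visits: 2.38/30 = 7.9% to 3.71/30 = 12.4%, or 0.32 to 0.50 subjects.

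**The case against.** The best reply is that this is mostly wording. In 9.2.1 the adverse event cut-off is completion of the visit, and the day range is only in parentheses. A subject seen on Day 20 or Day 38 still has events documented through that contact. The two 19-39 ranges may be one nominal window with a loosely stated anchor. This stands as far as it goes: for non-serious events the collection period ends at the visit by definition, so the direct tension is with the SAE period alone.

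A reader might infer that SAEs are lost, or that 9.2.2 is contradicted. The documents do not support that. The duty in 9.2.2 depends on the site's awareness, requires no query at day 30, and also covers later SAEs considered at least possibly drug-related. Known events are followed until resolved, chronic or stable (9.2.1.2), and clinically significant laboratory results are followed too (9.2.3). What is missing is solicitation of new events.

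A reader might also count the Day 30 reference in 7.1 as a fourth conflicting window. It only names the assessments for an early-withdrawal visit. Its gap is 1 day, or 0 if Day 30 means 30 days post-dose.

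Finally, Attachment A, part of SAP 7.1.2 and the SAP table list are not readable here. Attachment A may state a governing window or a further contact. It could not, however, make the body sections agree with one another.

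**Conclusion.** The point holds as a minor one. Three windows for the same contact disagree, and each permits the last planned query well before the SAE period closes. The day counts rest only on the protocol's own numbering. The sizing rests on the assumed 10% risk, front-loading and spread of visits, and stays below one subject in every scenario tried, including the extreme one in which everyone is seen on the earliest day.

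It would be going too far to conclude that the safety percentages are materially distorted. The safety analysis is descriptive, the trial has a single arm and so no between-arm bias, and the efficacy endpoints are untouched. The reason to act is that sites need one instruction and the remedy is cheap.

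**What to change.** **Protocol.** State one window, counted from dosing, in the synopsis, Section 3, 6.1.7, 7.1, 9.2.1, 9.2.1.2 and SAP 3. Put the final phone or telehealth contact at or after 30 days post-dose, for example Days 31-41. That is 30 to 40 days post-dose, and at the latest 40 - 1.5 = 38.5 to 40 - 0.5 = 39.5 days post-surgery, close to the present limit. Alternatively, keep the earlier visit and add a brief call on or after Day 31. Either removes the solicitation gap for subjects who are reached.

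**SAP.** Keep all TEAEs in the main tables as SAP 9.1 now defines them. Cutting those tables off at 30 days would drop observed events that the plan currently includes. Add a supplementary summary of serious TEAEs and deaths with onset through 30 days post-dose, and report how many subjects had a contact at or after that day. These SAP additions remain useful even if some final visits have already taken place.

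**Tidying.** The follow-up sentence in 6.1.7 points to Section 10.2.2; the SAE text is in 9.2.2.

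**Cost.** Wording changes in both documents, a window of 11 days instead of 21 or 15, an upper limit 2 days beyond 6.1.7 and 5 beyond 9.2.1, slightly more late or missed contacts, and one extra short call for some subjects. The final contact is only a medication review and an adverse event query and may already be done by telehealth, so the burden is small.

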## **7. STOPPING THE STUDY OR EARLY WITHDRAWAL OF SUBJECT**

This study may be stopped (terminated) by the Sponsor at any time and for any reason. Subjects on study at the time the study is stopped will be asked to complete all assessments in the Early Termination visit (see Attachment A).

**NOTE: The study may also be stopped or delayed by the DSC as outlined in Section 9.1.2.**

### **7.1 Individual Subject Withdrawal**

The participation of an individual subject in the study may be terminated in the following circumstances:

1. Withdrawal of informed consent by the subject.
2. Any occurrence that, in the Investigator's opinion, makes continued participation contrary to the subject's best interests.

If an Investigator removes a subject from the study, or if a subject declines further study participation, an Early Withdrawal Visit, consisting of the assessments required at the Day 30 visit, will be completed as soon as possible. It will be the responsibility of the Investigator to ensure that all withdrawn subjects receive appropriate follow-up and medical care if needed.

## **8. EFFICACY EVALUATIONS**

Intra-operative and post-operative evaluations will be used to support the efficacy endpoints of the study.

**8.1 Primary Efficacy Assessments:**

[REDACTED]

**8.2 Secondary Efficacy Assessments:**

[REDACTED]

**8.3 Intra-operative Evaluations**

[REDACTED]

**8.4 Post-operative Evaluations**

Following completion of surgical procedures and imaging, the surgical specimen will be sent to the study pathologist who will conduct standard histological assessment of the surgical specimens. (See Pathology Manual)

**9. SAFETY EVALUATIONS**

**9.1 Data Safety Committee (DSC)**

**9.1.1 Constitution of the DSC**

A Data Safety Committee will be appointed by Vergent Bioscience and will include at a minimum:

- The Principal Investigator
- The Vergent Medical Monitor
- An Independent Physician Reviewer
- The Project Statistician

[REDACTED]

